9.2. Setting

The study will be conducted in the outpatient setting in Germany.

Study population

All patients with a record of Flupirtine prescription during the defined 12-month periods (patient selection window) will be identified from selected database.

The study will include both single users and recurrent users of flupirtine-containing medicinal products.

The study will include two cohorts of patients:

- patients initiated on flupirtine treatment after the review of SmPC in Germany
- patients treated with flupirtine before the review of SmPC in Germany

The two cohorts will include:

- Incident user: patients who had one or more flupirtine prescriptions during the one-year observational period, but no flupirtine prescription for at least 12 months prior to the first flupirtine prescription during the observational period
- Prevalent user: patients who had one or more flupirtine prescriptions during the one-year observational period and at least one flupirtine prescription during the 12 months prior to the first flupirtine prescription during the observational period

Inclusion criteria:

Eligible patients must have at least one prescription of Flupirtine (exposure) during the defined 12-month observational period.

Exclusion criteria:

Exclusion criteria will not be applied.

Study period

The selection of patients from the IMS[®] Disease Analyzer will be carried out in two defined 12-month periods from January 1, 2012 to December 31, 2012 and January 1, 2014 to December 31, 2014, respectively (patient selection window). The date of the first prescription fill in each period will be defined as the exposure start date.

Pre-exposure period:

In order to obtain information about medical history before Flupirtine exposure start, a time period of at least 12 months prior to the individual Flupirtine exposure start date will be analysed for each patient for whom these data are available.

Follow-up:

A follow-up period of one to six months after the exposure start date will be monitored for all patients, and till the end of analysis period for whom these data are available.

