9.5. Study size

All patients in the PCP and orthopaedist panel of the IMS[®]DA fulfilling the selection criteria will be considered for the study.

A preliminary count of patients treated with Flupirtine over a 12-month period (July 2013 to June 2014) gave the sample sizes for the selected IMS[®] DA panels (presented in Table 2). As acute pain treatment has no seasonal impacts, the 12 months period and not a calendar year period is acceptable for feasibility appraisal.

Table 2: Number of patients with flupirtine-containing prescriptions in the IMS[®] Disease Analyzer from July 2013 to June 2014

IMS [®] DA Panel	Number of Flupirtine patients	Number of Flupirtine patients with at least 12 months history	Number of Flupirtine patients with at least 12 months history (25% reduction)
PCP	14,743	11,284	8,463
Orthopaedist	4,635	1,821	1,365

Taking into account the sample sizes and a further 25% reduction for a hypothetical decrease in Flupirtine prescriptions over the planned observation period compared to the period evaluated in 2014, we expect that the minimum number of Flupirtine patients available for the analysis will be not lower than about 8,400 and 1,300 patients in the DA PCP and orthopaedist panel, respectively. The more data are available, the higher the level of confidence on any estimates, i.e. the smaller the width of the 95% confidence interval.

Similar Flupirtine patient counts for the DA database are expected for the 12-month selection window of the Flupirtine DUS.

The study size of the Flupirtine DUS is expected to range from approximately 1,300 Flupirtine patients in the orthopaedist panel of the IMS[®] DA database. The study size is based on the number of patients with Flupirtine prescriptions in the 12-month period from July 2013 to June 2014, so the study size of the planned 12-month patient selection window in the Flupirtine DUS may be slightly different.

The 12-month patient selection window is considered to be sufficient to provide representative for prescribing practices during the routine clinical use of flupirtine-containing medicinal products in Germany.

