9.7.2.1 Patient characteristics of Flupirtine treated patients

The patient characteristics (age, gender, insurance private or SHI) of Flupirtine patients will be described.

- Number of patients within following age groups:
 - < 18 years
 - 18 to 29 years
 - 30 to 39 years
 - 40 to 49 years
 - 50 to 59 years
 - 60 to 69 years
 - 70 years and older

Analyses:

- Number and percentage of Flupirtine patients per age group, gender, insurance status(private or SHI insured)

Indication for flupirtine prescription

In order to describe the indication for flupirtine drugs all diagnoses related to the flupirtine prescriptions will be analysed.

- All diagnoses documented on the prescription of flupirtine will be defined as principal diagnosis.

As not for all prescriptions principal diagnoses will be available, additionally the following approaches will be chosen:

- If there is any disease associated with acute pain (Annex 3-ii) recorded in a time frame of 2 weeks around the date of prescription, this will be defined as associated diagnosis.
- If there is any disease associated with acute pain (Annex 3-ii) recorded in a 12 months history before the date of prescription, this will be defined as co-morbidity.

Principal diagnoses, associated diagnoses and co-morbidities will be analysed separately.

The findings of principal diagnoses will be grouped by diagnosis according to ICD-10 codes (selection of codes see Annex 3) including diseases associated with acute pain and chronic pain.

Analysis:

- Number and percentage of prescriptions, stratified by diagnosis (only principal diagnoses)
- Number and percentage of prescriptions associated with acute pain (principal diagnoses, associated diagnoses and co-morbidities)
- Number and percentage of prescriptions associated with chronic pain (only principal diagnoses)

Contraindication for the use of NSAIDs or weak opioids

The patients' history will be evaluated for medical events referencing to contraindications for NSAIDs or weak opioids (such as myocardial infarction or stroke) for a timeperiod of 12 months prior to first prescription of Flupirtine. Only patients with a history of at least 12 months will be included in this analysis.

Analyses:

- Number and percentage of patients identified as contraindicated of NSAIDs/weak opioid treatment (such as myocardial infarction or stroke)

Long-term medications leading to contraindications for Flupirtin

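### Incident status does not require 12 months of observable history, while the study size counts only patients who have it

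*Protocol*

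**What the plan says.** **Eligibility (9.2).** The single inclusion rule is "Eligible patients must have at least one prescription of Flupirtine (exposure) during the defined 12-month observational period". The next line reads "Exclusion criteria will not be applied". Neither mentions length of record.

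**Strata (9.2, repeated in 9.7.2).** Incident users had a prescription in the window "but no flupirtine prescription for at least 12 months prior to the first flupirtine prescription during the observational period". Prevalent users had "at least one flupirtine prescription during the 12 months prior to the first flupirtine prescription during the observational period". There is no third group.

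**Look-back (9.2).** The 12-month pre-exposure period "will be analysed for each patient for whom these data are available", so patients with less history stay in.

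**Use of the split.** Sections 9.7.1 and 9.7.2 stratify all analyses by incident and prevalent use. Section 9.7.2.4 does the same for the 2012 versus 2014 comparisons, by panel.

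**Where history is required.** Section 9.7.2.1 says of the NSAID/weak-opioid contraindication analysis: "Only patients with a history of at least 12 months will be included in this analysis". No other analysis carries this condition.

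**Study size (9.5).** From the Table 2 column restricted to patients with at least 12 months of history, less 25%, the protocol concludes that "we expect that the minimum number of Flupirtine patients available for the analysis will be not lower than about 8,400 and 1,300 patients" in the PCP and orthopaedist panels. Section 9.9 adds that medical history will be evaluated for at least 12 months, without making this a condition of entry.

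**The concern.** Absence of a record means absence of use only where use could have been recorded. Prevalent status needs a positive earlier prescription. Incident status needs only that none is found, so patients with a short record drift into the incident stratum.

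The parameters at risk are those that show whether the two-week restriction was followed: single versus repeated prescriptions, length of treatment episodes, and the share of patients with an episode over 14 days. Ongoing users counted as new would tend to raise all three in the incident stratum. If completeness of history differs between 2012 and 2014, the before-after contrast in that stratum could also move without any change in prescribing.

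Separately, sections 9.2 and 9.5 describe different populations, so a reader cannot tell which one the tables will cover.

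**Working it through.** **Inputs (Table 2, section 9.5, July 2013 to June 2014).**

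| Panel | All patients (N) | At least 12 months of history (H) | After 25% reduction |
|---|---|---|---|
| PCP | 14,743 | 11,284 | 8,463 |
| Orthopaedist | 4,635 | 1,821 | 1,365 |

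**1. The protocol's own figures.** H × 0.75: PCP 11,284 × 0.75 = 8,463; orthopaedist 1,821 × 0.75 = 1,365.75, shown as 1,365. Both reproduce. The text rounds them down to about 8,400 and 1,300 as a floor.

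**2. Patients without 12 months of history.** L = N − H.
- PCP: 14,743 − 11,284 = 3,459; 3,459 / 14,743 = 23.5%.
- Orthopaedist: 4,635 − 1,821 = 2,814; 2,814 / 4,635 = 60.7%.

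These are the largest shares of panel patients that could be called incident without a verifiable look-back. The true share is lower to the extent that short-history patients show an earlier prescription and so count as prevalent.

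**3. Unverified share of the incident stratum (assumed inputs).** Let q be the prevalent share among patients with full history and r the share of short-history patients with a recorded earlier prescription. The documents give neither. The share is L(1 − r) / [H(1 − q) + L(1 − r)].

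| Panel | r | q = 0 | q = 50% |
|---|---|---|---|
| Orthopaedist | 0 | 2,814 / 4,635 = 60.7% | 2,814 / 3,724.5 = 75.6% |
| Orthopaedist | 25% | 2,110.5 / 3,931.5 = 53.7% | 2,110.5 / 3,021 = 69.9% |
| PCP | 0 | 3,459 / 14,743 = 23.5% | 3,459 / 9,101 = 38.0% |
| PCP | 25% | 2,594.25 / 13,878.25 = 18.7% | 2,594.25 / 8,236.25 = 31.5% |

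Over this range, more than half of the orthopaedist incident stratum would have unverified status.

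**4. Size under the section 9.2 rule.** N × 0.75: PCP 14,743 × 0.75 = 11,057; orthopaedist 4,635 × 0.75 = 3,476. Against 8,463 and 1,365, the eligible population is 1.3 and 2.5 times the one used for sizing (11,057 / 8,463; 3,476 / 1,365).

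**5. Is a 12-month requirement implied?** The explicit restriction in the NSAID/weak-opioid analysis would be redundant if it applied throughout. Section 9.2 uses history where it exists. Sections 9.5 and 9.9 suggest that 12 months was intended, but no eligibility or classification rule carries that through.

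**The case against.** **Unverified is not wrong.** A reader might infer that 61% of orthopaedist patients are misclassified. The documents do not support this: many short-history patients may be genuine new users, and one with 11 months of record can still show an earlier prescription. A reader might also go on to estimate how many labelled incident are really prevalent. Taking a prevalent share p of 20% to 40%, equal in short- and long-history patients, with no earlier use detected in any short-history patient, 2,814p / [1,821(1 − p) + 2,814] gives 13% to 29% for orthopaedists. None of those three inputs is in the protocol, and the last is extreme. This objection stands.

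**Twelve months of history does not prove incident status either.** Section 9.9 says patients cannot be followed across panels and care outside the practice is not recorded. The protocol also does not define how history is established for Table 2. This stands too, and limits what any fix can achieve.

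**Not every comparison is exposed, and period bias is conditional.** The NSAID/weak-opioid analysis has its own restriction. Panels are never combined, so a difference between panels does not itself bias a before-after comparison. No figure shows that history completeness changed between 2012 and 2014. All correct.

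**The study size is a floor and no test depends on it.** True: 11,057 and 3,476 satisfy a minimum of 8,400 and 1,300, and the study is descriptive. But a larger count reached by admitting different patients does not make the two sections agree.

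**The analysis plan could settle it.** A history flag is often specified there. Here, however, the eligibility rule, the two definitions and the sizing population are all fixed in the protocol and do not fit together.

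**Conclusion.** The point holds as a defect of definition and an inconsistency between sections. Followed as written, the protocol puts patients whose earlier use cannot be checked into the incident stratum. They make up at most 60.7% of orthopaedist and 23.5% of PCP patients in the feasibility count. How many are ongoing users is unknown, as are the corresponding shares for 2012 and 2014. Distortion of repeat use, episode length and the over-14-day share among new users is the likely direction; distortion of the before-after contrast follows only if history completeness differs by period. The mismatch between sections 9.2 and 9.5 needs no assumption beyond the protocol's own 25% reduction.

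**What to change.** 1. Run the incident/prevalent stratified analyses and the section 9.7.2.4 comparisons on patients with at least 12 months of documented practice history before exposure start, and state how that history is established. Apply the condition to both strata. Keeping short-history patients who show an earlier prescription while dropping those who do not would inflate the prevalent share.
2. Report patients with under 12 months of history as a separate group, with counts per panel and period, and show all-patient results alongside.
3. Make sections 9.2, 9.5 and 9.9 consistent and say which population the study size refers to.
4. State in section 9.9 that prescribing in other panels or practices remains unobservable and so limits incident status even with 12 months of history.

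**Cost.** This is a wording change plus a history indicator that Table 2 shows can already be derived. The stratified population falls to the section 9.5 totals. Those cover incident and prevalent patients together, so the incident stratum alone will be smaller. If 20% to 40% are prevalent (an assumed range), the orthopaedist incident stratum is 1,821 × 0.80 × 0.75 = 1,093 down to 1,821 × 0.60 × 0.75 = 819, or about 820 to 1,090 patients. The restriction may also remove many patients new to a practice, which is why the all-patient results should be shown as well.

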9.3. Variables

The following variables will be derived from the data sources.

IMS[®] Disease Analyzer – PCP and orthopaedist panels

- Number of prescribing physicians
- Region of office (East/West Germany)
- Number of overall patients in the office
- Number of patients with at least one prescription of flupirtine-containing medicinal product
- Patient characteristics
 - Age
 - Gender
 - Insurance status (private or SHI insured)
 - Indication for Flupirtine exposureⁱⁱⁱ
- Flupirtine exposure
 - Number of Flupirtine prescriptions per patients during the observation period
 - Single use and repeated prescriptions
 - Treatment duration (by physician)
 - Dosage advice (by physician)
 - Prescription length (based on DDD or on physician's advice if available)
 - Co-diagnosis during study period
 - Concomitant prescription of drugs grouped by relevant ATC classesⁱⁱ
- Long-term medications (>14 days) leading to contraindication for Flupirtine
- Diseases contraindicated for NSAIDs and weak opioids
- Liverfunction tests - as far as available within 1 week after Flupirtine exposure

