The study will capture patients in the outpatient setting in Germany. All patients who have received at least one prescription for a flupirtine-containing product within a defined 12-month period (patient selection window) in the selected data sources will be included in the analysis. The analysis will consist of 2 time periods, the first one the year 2012 as time frame before and the second one the year 2014 as time frame after the SmPC revision.

Variables

The following variables will be extracted from the database:

- Prescription of a flupirtine-containing medicinal product
- Specialty and type of prescribing physician

- Demographical characteristics of patients treated with flupirtin (age, gender, insurance)
- Indication for Flupirtine treatment (reasons for prescription)
- Duration of Flupirtine treatment recommended by the physician
- Daily Flupirtine dose recommended by the physician
- Prescription length
- Concomitant prescriptions of drugs
- Co-diagnosis
- Liverfunction tests

Data sources

The following data sources will be used: IMS[®] Disease Analyzer (DA); primary care physician (PCP) and orthopaedist panels. Both panels cover more than 95% of all Flupirtine prescriptions in Germany.

Study size

All patients in the PCP and orthopaedist panel recorded during the analysis periods 2012 and 2014 of the IMS[®] DA will be considered for the study. The study size per period will include approximately 1,300 patients treated with Flupirtine in the orthopaedist panel of the IMS[®] DA database and approximately 8,400 patients treated in the PCP panel.

Data analysis

The statistical analysis will be done descriptively and performed separately for each physician panel. All analyses will be stratified by incident and prevalent users. Missing values will be reported as missing and no imputation will be conducted. Descriptive tables will be made for all variables.

Milestones(planned)

Start of data collection (reference period):	January 1, 2012
End of data collection (reference period):	December 31, 2012
Start of data collection (assessment period):	January 1, 2014
End of data collection (assessment period):	December 31, 2014
Registration in the EU PAS register:	Registration is planned prior to study initiation once the protocol is final and approved by BfArM
Final study report:	February 29, 2016

During the analysis time the following points and related time periods required have to be taken into account:

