9.7 Data analysis

9.7.1 General remarks

Data from specialist panels will not be combined. The data will be analysed separately by panel (PCP and orthopaedist panel) and for the period before and after SmPC review.

All analyses will be stratified by incident and prevalent users.

Study tables will reference the data source used for each set of results. The data will be presented graphically where useful.

The statistical unit will be the patient (for information such as demographical and clinical characteristics, medical history, contraindications) and the Flupirtine prescription (for information such as indication, number of prescriptions, recommended treatment duration, concomitant drug prescriptions).

The statistical analysis will be done descriptively. Missing values will be reported as missing and no imputation will be conducted. Descriptive tables will be compiled for all variables. Continuous variables will be presented with counts, means, medians, standard deviations, and minimum and maximum values. Categorical variables will be presented in frequency tables. Rates and 95% confidence intervals will be provided when relevant.

Data will be analysed using the statistical software SAS (SAS Institute Inc., Cary, USA) with version 9.3 or above.

All results will be presented in tables. In addition, parameters addressing the primary objectives and eligible for a comparison of time periods (assessment period and reference period) with respect to the effect of risk minimisation measures (for example flupirtine treatment duration) will be presented graphically e.g. by displaying plots or bar charts.

The following section will describe the analyses and definitions used for the DA (**IMS[®] Disease Analyzer**) database.

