9.7.2.2 Flupirtine exposure

Flupirtine exposure will be defined as one or more prescriptions of Flupirtine. These prescriptions will be identified using the ATC code for Flupirtine or INN. The Flupirtine exposure start date (i.e. the cohort entry date) for each patient will be defined as the date of the first record of Flupirtine prescription during each of the defined twelve-month patient selection window.

Treatment duration

The treatment duration (in days) will be evaluated by using the recommended treatment duration by the physician. If this is not available, the treatment duration cannot be determined exactly as the dose recommendation “as required (pro re nata)” is very often given in the therapy of acute pain. Therefore, the percentage of patients with no information according to recommendation by the physician will be determined.

Prescription length

The prescription length (in days) will be determined as follows:

- For prescriptions with available information on recommended dose per day: from the prescription date plus the expected number of days of drug supply based on the package size and the recommended daily dose
- For all prescriptions without recommendation of dosage: from the prescription date plus the expected number of days of drug supply based on the package size and the DDD(400 mg / day)

The prescription length is therefore not necessarily identical to the treatment duration.

The following parameters will be considered in the analysis for each Flupirtine prescription:

- Date of prescription
- Recommended daily dose by physician
- Recommended treatment duration by physician

Analyses:

- Number and percentage of patients with prescriptions of a flupirtine-containing medicinal product during the 12-month patient selection window
- Treatment duration in days
- Prescription length
- Single use and repeated use

Treatment episodes

A treatment episode will be defined as one or more prescriptions (repeated prescriptions) of flupirtine with gaps between prescription length not more than 7 days. In the case the gap between the prescriptions is longer than 7 days it will be considered as two subsequent treatment episodes. The analysis of treatment episodes will consider prescription length based on DDD, because for all prescriptions this information will be available.

Analyses:

- Number and percentage of episodes
- Min, max, mean, median length of episodes
- Patients within each episode

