9.9. Limitations of the research methods

IMS[®] Disease Analyzer is representative of Germany as a whole insofar as that the included practices are selected to adequately reflect geographic coverage and differences between urban and rural locations. This database contains information from approximately 3,000 office-based physicians (including specialists) who represent approximately 2.4% of all practices in Germany. The balance of various specialties in the IMS[®] Disease Analyzer does not, however, exactly reflect the balance in Germany. The lack of data from Flupirtine-prescribing oncologists will limit only to some extent the representativeness of results. For the characterization and comparison of the prescribing practice, however, this does not pose a problem.

The limitations of the IMS[®] Disease Analyzer are those of a provider-sourced EMR database. Patients seeking care outside the EMR practice setting will not have that utilisation recorded in the database. One of the main reasons for data documentation is reimbursement purposes. In the IMS[®] Disease Analyzer patients cannot be tracked across panels. Therefore, patients cannot be followed up across specialties and double counting of patients cannot be completely ruled out when analyzing more than one panel. It is planned to use of the PCP and the orthopaedist panels for this study.

For patients covered in the IMS[®] Disease Analyzer the medical history of patients will be evaluated for at least 12 months.

The duration of Flupirtine treatment (in days) will be evaluated using the treatment duration recommended by the physician. In cases where this information is not available, the treatment duration will be calculated using recommended dosage by the physician. The dose recommendation “on demand (pro re nata)” is very often given in the therapy of acute pain, acute pain episodes, and acute pain exacerbations which occur repeatedly. Therefore, the actual treatment duration is often shorter compared to the length of prescription.

The length of prescription will be determined from the recommended daily dose by the physician (if available) or using the defined daily dose (DDD). The dose recommendation “on demand” will not be taken into account for the determination of prescription length.

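### Prescription length mixes recorded-dose and DDD-assumed values, so its 2012 and 2014 tables could differ through dose recording alone; the listed pre-post duration measures are not affected

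*Protocol*

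**What the plan says.** Section 9.7.2.2 of the protocol derives prescription length by two rules.

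- "For prescriptions with available information on recommended dose per day", the supply in the package is divided by that recommended dose.
- "For all prescriptions without recommendation of dosage", it is divided by a fixed value, taken from "package size and the DDD(400 mg / day").

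Section 9.3 states the same definition in short form ("Prescription length (based on DDD or on physician's advice if available")), and Section 9.9 repeats it: "The length of prescription will be determined from the recommended daily dose by the physician (if available) or using the defined daily dose (DDD"). The mixed rule is therefore deliberate.

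The missing-data rule in Sections 4 and 9.7.1 is general: "Missing values will be reported as missing and no imputation will be conducted". No exception is made for the DDD rule.

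Prescription length is a listed item in Sections 4 and 8 and a listed analysis in Section 9.7.2.2. On reporting, Section 9.7.1 says: "The data will be analysed separately by panel (PCP and orthopaedist panel) and for the period before and after SmPC review". It also stratifies all analyses by incident and prevalent use.

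Treatment episodes are handled differently. Section 9.7.2.2 bases them on the DDD for every prescription, giving as its reason that this is available throughout. Section 9.7.2.4, which lists the parameters for comparing the two periods, includes episode length and the share of patients with any episode beyond 14 days (DDD basis). It does not include prescription length.

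**The concern.** A mean or median of this variable summarises two kinds of value together: a supply length based on the physician's dose, and a supply length based on an assumed dose. The mixture depends on how often a dose is recorded. If that share differs between 2012 and 2014, the summary can move although prescribing has not changed.

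The study has a pre-post design, and prescription length will be available side by side for the two years in each panel. A reader could take a difference in that table for a change in the amount prescribed per prescription.

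The wording is a second problem. Substituting 400 mg/day for an unrecorded dose acts as a single-value fill, and the protocol does not say how this fits with its no-imputation sentence.

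**Working it through.** The protocol states no figure that could be reproduced here, so the check is of the mechanism.

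**Inputs from the protocol:** DDD of 400 mg/day (Section 9.7.2.2); the two-rule definition (Sections 9.3, 9.7.2.2, 9.9); reporting by period and panel (Section 9.7.1).

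**Assumed inputs, not in the protocol:** a supply of 4,000 mg per prescription; a share f of prescriptions with a recorded dose, rising from 30% to 50%; a recorded dose d between 200 and 600 mg/day. The doses serve the arithmetic only. Supply, recorded doses and prescribing are held the same in both years, and recorded dose is taken as unrelated to pack size. Where recorded doses vary, d is their harmonic mean, because length is proportional to 1/d.

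**Formulas**

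- DDD-based length: L = supply / 400 = 4,000 / 400 = 10.0 days.
- Mixed mean: L × [1 + f × (400/d − 1)].
- Shift when f moves from f1 to f2: L × (f2 − f1) × (400/d − 1).

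**Worked cases**

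- d = 300: 10 × [1 + 0.3 × 0.333] = 11.0 days, and 10 × [1 + 0.5 × 0.333] = 11.67 days.
- d = 600: 10 × [1 − 0.3 × 0.333] = 9.0 days, and 10 × [1 − 0.5 × 0.333] = 8.33 days.

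| Recorded dose d (mg/day) | Mixed mean, f = 30% | Mixed mean, f = 50% | Change | DDD for all: change |
|---|---|---|---|---|
| 200 | 13.0 d | 15.0 d | +15.4% | 0 |
| 300 | 11.0 d | 11.67 d | +6.1% | 0 |
| 400 | 10.0 d | 10.0 d | 0 | 0 |
| 500 | 9.4 d | 9.0 d | −4.3% | 0 |
| 600 | 9.0 d | 8.33 d | −7.4% | 0 |

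The percentage changes do not depend on the assumed supply, since L cancels. A fall in recording reverses the sign: from 50% to 30%, the change is −5.7% at d = 300 and +8.0% at d = 600.

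The shift is zero if recording is stable (f1 = f2) or if d = 400. It needs both a change in recording and a recorded dose that differs from the DDD.

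**Section 9.7.2.4 measures.** Episodes use supply / 400 for every prescription, so f and d do not enter. A change in dose recording moves episode length and the share beyond 14 days by exactly 0.

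**The case against.** The strongest answer is that the protocol already protects the comparison that matters. Section 9.7.2.4 omits prescription length and uses DDD-based episodes, which cannot be moved by dose recording. A reader might infer from the mixed definition that the 2012 versus 2014 conclusions on duration are distorted. The protocol does not support that; the exposure is confined to the prescription-length tables and to any graph of them that Section 9.7.1 would permit.

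A reader might also infer that the share of assumed values will stay hidden. That goes too far. Recommended daily dose is a variable in its own right, and Section 9.7.1 calls for descriptive tables of all variables with missing values shown, so its missing count should appear by panel, period and user status. What stands is that nothing places this count beside the length table. It may also not match exactly the share that falls back on the DDD, because Section 9.9 sets on-demand dose advice aside when prescription length is derived.

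On imputation, the fallback is prespecified, openly stated and listed among the limitations, and the dose field itself is not overwritten. The conflict is largely one of wording. It still needs a sentence, because the rule as written admits no exception.

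Finally, nothing in the protocol shows that recording changed. The risk-minimisation measures it describes concern indication, duration, contraindications and liver tests, not dose documentation. That stands, and it is why the size must be left open. The layout of a descriptive table could also be settled in the statistical analysis plan mentioned in Section 9.8, which is not available here; but the mixed definition and the blanket no-imputation sentence are both fixed in the protocol.

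**Conclusion.** The point holds in a limited form. Prescription length is a mixed variable, its DDD fallback is not reconciled with the no-imputation sentence, and its 2012 and 2014 summaries are on one scale only if dose recording is stable or recorded doses average harmonically 400 mg/day. The protocol supplies no information on either condition, so the size is unknown. Under the assumed rise in recording from 30% to 50%, the artefact ranges from −7.4% to +15.4% for recorded doses of 600 down to 200 mg/day. These figures show what the rule can do; they do not estimate what happened. The listed pre-post duration measures are unaffected. Priority: minor.

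**What to change.** In Section 9.7.2.2, replace the single variable by two:

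- (a) DDD-based length for all prescriptions, used for any display of prescription length that sets 2012 against 2014;
- (b) recorded-dose length, only for prescriptions with a recorded dose.

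Beside them, show n and % of prescriptions with a recorded dose, per panel, period and user status. Align the wording in Sections 9.3 and 9.9. In Sections 4 and 9.7.1, state that the DDD-based length is an explicit exception to the no-imputation rule and rests on an assumed daily amount.

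The cost is a few lines of text and a small extension of the table shells, with no new data. The downside is two length figures instead of one.
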